Data will be presented with descriptive statistics. Cumulative incidence curves will be created to analyze engraftment and acute GVHD. Death will be treated as a competing event. Probability of overall survival and event-free survival will be estimated with Kaplan-Meier curves.

3. Stopping Rules:

A predictive probability design (Lee, Lin. Clinical Trials. 2008) will be used to control for safety with respect to TRM. The unacceptable rate of TRM is 30% or more. This will be tested against a one-sided alternative. The trial will initialize by enrolling 10 patients. If 3 or more out of 10 have a TRM the trial will stop.

Otherwise the trial will continue according to the stopping rules plan (Appendix 2) up to a maximum of 73 patients. If the number of patients with a TRM within 100 days following allogeneic HCT is ever greater than or equal to the number listed in the corresponding patients enrolled row the trial will stop and the drug will be declared not safe. This design yields a type I error rate 0.05 and power greater than 80% when the true rate of TRM is 15%. Note the stopping rule must be made based on the chronological order of the patients enrolled.

We plan to meet with medical monitor approximately every quarter to review these safety data and stopping rules. The medical monitor will review the TRM data in the context of HLA mismatch; and as usual, he/she will have the final authority regarding continuation of the study in the event of excessive TRM.

VIII. REGULATORY, ETHICAL, AND STUDY OVERSIGHT CONSIDERATIONS

The protocol and informed consent document for this study must be approved in writing by the Institutional Review Board (IRB) prior to any patient being registered on the study.

Changes to the protocol must also be approved by the IRB. Records of the Institutional Review Board review and approval of all documents pertaining to this study must be kept on file by the investigator and are subject to FDA inspection at any time during the study. Periodic status reports will be submitted to the Institutional Review Board at least yearly, as well as notification of completion of the study and a final report within 6-12 months of study completion or termination. Informed consent will be obtained prior to the treatment of participants.

1. Data Safety Monitoring Plan:

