APPENDIX 2: STOPPING RULES PLAN

Patients Enrolled	Stop if # with TRM within 100 days following HCT is greater than or equal to
10	3
11	3
12	3
13	4
14	4
15	4
16	5
17	5
18	5
19	5
20	6
21	6
22	6
23	6
24	7
25	7
26	7
27	7
28	7
29	8
30	8
31	8
32	8
33	9
34	9
35	9
36	9
37	9
38	10
39	10
40	10
41	10
42	11
43	11
44	11
45	11
46	11

47	12
48	12
49	12
50	12
51	12
52	12
53	13
54	13
55	13
56	13
57	13
58	14
59	14
60	14
61	14
62	14
63	14
64	14
65	15
66	15
67	15
68	15
69	15
70	15
71	15
72	15
73	15

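### The TRM stopping rule has no boundary below 10 patients, so read literally it stays silent on a third early TRM that already commits row 10 to being crossed

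*Combined protocol and SAP*

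**What the plan says.** Section VII.3 (Stopping Rules) opens the rule with "The trial will initialize by enrolling 10 patients" and continues "If 3 or more out of 10 have a TRM the trial will stop". After that, "Otherwise the trial will continue according to the stopping rules plan (Appendix 2) up to a maximum of 73 patients". The count is compared with the row for the number of patients enrolled, and "Note the stopping rule must be made based on the chronological order of the patients enrolled".

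The Appendix 2 column is headed "Stop if # with TRM within 100 days following HCT is greater than or equal to". It has 64 rows, from 10 to 73 patients. The boundary is 3 at rows 10 to 12 and rises to 15 at rows 65 to 73. There is no row below 10.

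Other controls apply at any number of patients:

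- **Section VIII.1 (Data Safety Monitoring Plan), accrual hold.** Accrual halts for any attributable serious adverse event until the medical monitor approves resumption in writing.
- **Section VIII.1, review.** The monitor reviews deaths associated with the protocol, recommends on continuation, and meets the investigator about every three months or more often.
- **Sections VII.3 and VIII.1, authority.** The monitor has the last word on continuation if TRM is excessive.

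**The concern.** A cumulative TRM count does not fall unless a death is later reclassified. Once three TRMs are known among the first 3 to 9 patients, the row-10 condition of 3 or more will be met whatever happens to the patients still to come. Those patients cannot change what the rule says, yet with fewer than 10 enrolled there is no row with which to compare the count.

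The usual reason for a minimum number before the first look is to avoid deciding on too little data. That reason does not apply once the rule's answer is fixed. At stake is the exposure of up to seven further patients (10 − 3) to a procedure that the plan's own boundary is about to declare not safe. No error rate is affected.

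**Working it through.** **Inputs.** Unacceptable TRM rate 30%, acceptable rate 15%, one-sided test, stated type I error 0.05 and stated power above 80% (VII.3). Boundaries at rows 10 to 73 (Appendix 2). Accrual of up to 80 patients (IV.1a) over about 5 years (XII), so 80/5 = 16 per year. TRM window 100 days.

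**The plan's own figures first.** Type I error here is the probability of never stopping at a true rate of 30%; power is the same probability at 15%. An exact binomial recursion over the table, with a look after each patient from 10 to 73 and all outcomes known, gives 0.0123 and 0.623. The stated 0.05 and 80% are not reproduced. That is a separate matter and the present point does not depend on it. Stopping only when the count strictly exceeds the row value gives 0.032 and 0.816. That reading contradicts both VII.3 and the table heading, and under it a third early TRM would not settle row 10.

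**Step 1. How often the third TRM falls among the first 9 patients (outcomes known at once).** P(X₉ ≥ 3) = 1 − Σ C(9,k) pᵏ (1−p)⁹⁻ᵏ over k = 0, 1, 2.

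- p = 0.15: 1 − (0.2316 + 0.3679 + 0.2597) = 0.141
- p = 0.30: 1 − (0.0404 + 0.1556 + 0.2668) = 0.537

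**Step 2. How many patients are enrolled between that third TRM and patient 10.** The mean per trial is the sum of P(Xₙ ≥ 3) over n = 3 to 9.

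- p = 0.15: 0.0034 + 0.0120 + 0.0266 + 0.0473 + 0.0738 + 0.1052 + 0.1409 = 0.409. Given that the event occurs, 0.409/0.141 = 2.9.
- p = 0.30: 0.0270 + 0.0837 + 0.1631 + 0.2557 + 0.3529 + 0.4482 + 0.5372 = 1.868. Given that the event occurs, 1.868/0.537 = 3.5.

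**Step 3. Effect of adding rows 3 to 9 with boundary 3.**

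| True TRM rate | P(stop), table as is | P(stop), rows 3–9 added | Expected enrolment, as is | Expected enrolment, rows added |
|---|---|---|---|---|
| 15% | 0.377 | 0.377 | 52.4 | 52.0 |
| 30% | 0.988 | 0.988 | 16.2 | 14.3 |

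The stopping probability is unchanged because every trial stopped at rows 3 to 9 would have stopped at row 10.

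**Step 4. Allow for follow-up lag.** At 16 per year a patient arrives about every 365/16 ≈ 23 days and ten patients take about 7.5 months, against a 100-day window. Some third TRMs are therefore known only after patient 10 is in, so steps 1 and 2 are upper bounds. A simulation with Poisson arrivals and TRM times uniform over 100 days (both assumptions; the documents give neither) counted trials in which the third TRM occurs before the tenth enrolment:

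| True TRM rate | Earlier stop | Patients spared, mean over all trials |
|---|---|---|
| 15% | about 7% | about 0.2 |
| 30% | about 34% | about 0.9 |

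When an earlier stop does occur, it spares roughly two and a half patients.

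**The case against.** A reader might infer that the protocol requires accrual to go on after a third early TRM. It does not say so. VII.3 and Appendix 2 say only where the numeric rule starts, and the phrase about 3 or more out of 10 can be read as met at the third TRM. The supportable statement is that the documents do not say what happens.

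A reader might also infer that the trial's stop is certain from that moment. What is fixed is the boundary crossing. The monitor reviews TRM in the context of HLA mismatch and has final authority on continuation.

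The section VIII.1 controls can act before patient 10, and a fatal event is by definition serious (X.7). This part of the objection stands, but it does not close the gap. The hold depends on attribution, and X.8 separates events due to the study procedure from expected transplant complications, including several that can be fatal, so a TRM need not trigger it. The review of deaths carries no automatic hold. With meetings about every three months, some four patients (16/4) can enrol between two of them. The monitor's final authority applies equally from row 10 onward, so it does not explain why the numeric rule is silent before it.

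Finally, a minimum number before the first look is an ordinary design feature, no stated figure is wrong because of this one, and the realistic saving is small. All of that stands. It limits the weight of the point without removing the case for a change that costs nothing statistically.

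**Conclusion.** The point holds as a gap in the rule. Read literally, VII.3 and Appendix 2 do not trigger on a third TRM among the first 3 to 9 patients, although the row-10 boundary is then bound to be crossed, subject to the monitor's final authority. The other safeguards may lead to an earlier hold but do not guarantee one.

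The size is modest. The 14% and 54% probabilities assume that each outcome is known before the next enrolment. The lagged figures rest on 16 patients per year, Poisson arrivals, uniform TRM times and continuous application of the rule; if it were read only at quarterly reviews, the saving would be smaller. The argument also assumes that no TRM is later reclassified. The documents do not support a claim that the gap distorts type I error or power.

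**What to change.** 1. Extend Appendix 2 with rows 3 to 9, each carrying the existing row-10 boundary of 3.
2. State in VII.3 that the boundary is met as soon as the third TRM occurs among the first 10 patients, without waiting for the tenth enrolment. Word this for the period when no more than 10 patients are enrolled, so that it does not compete with later rows, where the table allows more than 3.
3. In VII.3 and VIII.1, say how meeting the boundary relates to the accrual hold for attributable events and to the monitor's final authority, so that the three provisions can be read together.

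The cost is seven table rows and a few sentences. The stopping probability, and hence type I error and power, stays the same, as does the maximum sample size. No new threshold is introduced.

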Table 1. PREVIOUS WORK DONE IN THE AREA

Study	Bertania et al³⁶	Balashov³⁷	Lang¹⁹	Maschan²⁰	Locatelli²¹
Year	2014	2015	2015	2016	2017
PMID	24869942	26187864	26039210	26808573	28588018
No of pts	23	37	41	33	80
Adult /pediatric	Pediatric	Pediatric	Pediatric	Pediatric	Pediatric
Disease Indication	Non-malignant disorders	Primary Immune Deficiencies	ALL (20) AML(9) MDS/JMML (3) Solid tumors (4) Nonmalignant (5)	AML	ALL, AML
Donor	Haplo	MUD (n=27) Haplo (n=10)	≥2 HLA loci-mismatched parents	MUD MMRD Haplo	Haplo
GvHD prophylaxis	None	Tac/MTX (n=34) Tac/MMF (N=2) CSA/MTX (n=1)	MMF until day +30	None	None
CD34+ Dose	15.8x10 ⁶ /kg (10.2-40.0)	11.7x10 ⁶ /kg (5.9-21.3)	14.9x10 ⁶ /kg	9x10 ⁶ /kg (3.8-21)	13.9x10 ⁶ /kg (6-40.44)
Alpha/beta Dose	4x10 ⁴ /kg (1-9.5)	10.6x10 ³ /kg (0.8-368)	16.9x10 ³ /kg	20x10 ³ /kg (2.9-126)	0.047x10 ⁶ /kg (0.002-0.099)
Gamma/delta Dose	9.4x10 ⁶ /kg (1.6-95.4)		11.0x10 ⁶ /kg	9x10 ⁶ /kg (1-30)	8.1x10 ⁶ /kg (0.86-56.7)
Neutrophil Engraftment	Day+13 (10-20)	Day +16 (11-28)	Day +10 (7-21)	Day +16	Day +13 (9-19)
GVHD	Grade 1-2: 3 pts No chronic	Grade 2: 7 pts Grade 4: 1 pt Chronic: 1 pt	Grade 2: 4 pts Grade 3-4: 6 pts Chronic: 9 pts	Grade 2-3:14 pts Chronic: 10 pts	Grade 1-2: 24 pts Chronic: 4 pts
Graft Failure	2 Primary 2 Secondary	2 Primary 8 Secondary	5		2
Malignancy Relapse			17 pts	10 pts	19 pts
Infection	Viral reactivations: 9	CMV: 16pts, 5 with disease	Not Reported	CMV Reactivation: 52% EBV Reactivation: 50%	Not reported
Survival	2yr OS 91% 2yr DFS 91%	2yr OS 97% 2yr EFS 68%	If in CR1-3: 100% If in active disease: 0%	2yr OS 68% 2yr EFS 60%	OS 72% 5 years

RATIONALE

Based on these results we propose the use of $\alpha\beta$ T-cell/CD19+ B-cell depleted stem cells in mismatched related and unrelated donor HSCT for malignant and nonmalignant disorders in pediatric and adolescent/young adult patients. Mismatched related donors provide an allogeneic HSCT option for essentially all patients in need of HSCT. This approach reduces the risk of acute GVHD and reduces the need for GVHD prophylaxis, either of which is poorly tolerated by certain patient groups. Additionally, transplantation can be performed without delay which can be critical in patients with high risk malignant disease or very severe non-malignant disorders requiring urgent treatment.

IV. RESEARCH PLAN

1a. How many subjects will be studied?

We will enroll up to 80 patients.

1b. How will subjects be selected for this study?

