Patients attending the CCHMC bone marrow transplant (BMT) clinic who meet the eligibility criteria will be offered the opportunity to participate in this research study. The study is open to all participants regardless of gender or ethnicity.

2a. Inclusion Criteria

Any patient requiring an allogeneic HSCT who lacks an HLA-genotypically matched related donor. Genotypically matched related donors are allowed when there is a clinical desire to avoid the use of GVHD prophylaxis medications.

2b. Exclusion Criteria

Prior allogeneic transplant with active acute or chronic GVHD, or life-threatening infection. Patients with a prior history of allogenic transplant without active GVHD or life-threatening infection can be considered.

2c. Patients Requiring Second Allogeneic HCT or Additional Aliquots of Stored Hematopoietic Stem Cell Product

Patients may receive additional TCRA/b CD19 depleted product(s) if clinically indicated.

3. Randomization

Not applicable.

4. Procedures

Pre-Infusion Patient Evaluation:

Patients enrolled on this protocol will undergo evaluation for disease status and organ function per institutional HSCT guidelines prior to starting conditioning regimen.

Donor Selection:

Transplant donors will be selected based on institutional guidelines/SOPs.

Treatment Plan:

[REDACTED]

[REDACTED]

Informed Consent:

Informed consent will be obtained for each study participant (stem cell transplant recipient) and/or parent or legal guardian as appropriate. The study will be explained to the study subject in lay terms, in their native language. The informed consent process will require written consent by the patient (if ≥ 18 yrs of age) or parent/legal guardian.

The investigator will be available to answer any questions that the patient or caregiver may have regarding procedures, risks and alternatives. The signed consent form will be maintained in the study subject's chart with a copy being placed in the patient's medical record.

Preparative therapy:

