We will report the Day +100 event-free survival of patients where an event is defined as death, primary graft failure, autologous recovery (<5% donor-derived cells in whole blood or in the cellular compartment of interest, i.e. T cells in patients with SCID), secondary graft failure, receipt of an additional hematopoietic cell

product other than for control of infection (Donor lymphocyte infusion or Virus-Specific T cell infusion), and second allogeneic HSCT.

Acute GVHD:

Clinical assessments for acute GVHD are frequently performed using Modified Glucksberg Criteria as in Appendix 1. We will collect clinical information regarding incidence and severity of acute GVHD. We will report the Day +100 cumulative incidences of acute GVHD grades II-IV and III-IV.

Chronic GVHD:

Clinical assessments for chronic GVHD are also frequently performed using NIH Consensus criteria. We will report the 1 year cumulative incidences of chronic GVHD.

GVHD-Free Survival:

Based on the presence or not of acute or chronic GVHD at 1 year, we will report GVHD-free survival at 1 year.

VI. OFF STUDY CRITERIA/CRITERIA FOR WITHDRAWING SUBJECTS

Subjects (or parents or legal guardians) have the right to withdraw from the study at any time and for any reason without prejudice to his or her future medical care by the physician or the institution.

Any subject who withdraws consent to participate in the study will be removed from further treatment and/or study observation immediately upon the date of request. The subject will be followed for safety purposes for at least 1 week after infusion of the stem cell product.

Criteria for Removal from Protocol Therapy:

- Patient withdrawal from protocol therapy

Off Study Criteria:

- a) Death
- b) Receipt of a second stem cell product
- c) Lost to follow-up

VII. STATISTICAL CONSIDERATIONS

1. Sample Size and Study Duration:

We chose a sample size of 80 patients based on estimates of patient need for access to T cell depleted grafts over 3-5 years at our Institution. All patients will be followed for primary and secondary endpoints for at least 100 Days following allogeneic HSCT, and 1 year data will be collected regarding survival and presence or absence of acute or chronic GVHD.

2. Statistical Considerations for Data Analysis:

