The study will be monitored closely by a medical monitor. This will be a qualified physician not associated with this particular protocol. The monitor will have expertise in basic hematology and conduction of clinical trials, and will have prior regulatory experience for similar studies. The monitor will work closely with the PI to monitor the participants on study. He/she will meet with the PI and review study data/progress approximately every 3 months; more often at the discretion of the PI and/or medical monitor.

The medical monitor will review the TRM data in the context of HLA mismatch; and as usual, he/she will have the final authority regarding continuation of the study in the event of excessive TRM. The medical monitor is required to review all unanticipated problems involving risk to subjects or others, unanticipated serious adverse events and all subject deaths associated with the protocol and provide an unbiased written report of the review.

At a minimum, the medical monitor should comment on the relationship of the event or problem, to participation in the study. Based on the review of these events, the monitor should make a recommendation regarding study continuation. Although the expected rate of serious toxicities will be low, any unanticipated attributable serious adverse event will be discussed with the medical monitor. If there are any attributable Serious Adverse Events, the study will stop accrual

pending review by the medical monitor. The study will resume patient accrual only if written approval is given by the medical monitor.

All decisions regarding study continuation, modification, or termination will be reported immediately or annually, as appropriate, to the IRB and other appropriate agencies. Reports for events determined by either the investigator or medical monitor to be possible or definitely related to study participation and reports of events resulting in death should be forwarded in compliance with current IRB policy and applicable federal regulations.

All reports from Medical monitor will be forwarded to Cincinnati Children's Hospital Medical Center IRB and other regulatory agencies as appropriate.

2. Blood Specimens:

There are no research blood specimens for this study.

3. Other Previously Approved Research Studies in Which the Projected Patient Population May Also Be Involved:

Patients may be additionally involved in other studies surrounding the care of patients undergoing allogeneic HCT.

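### The maximum sample size is 80 in IV.1a and VII.1 but 73 in the TRM stopping rule and Appendix 2, and no visible text reconciles them

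*Combined protocol and SAP*

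**What the plan says.** Section IV.1a states: "We will enroll up to 80 patients". Section VII.1 repeats the figure as the sample size and derives it from expected demand, not from a power calculation: "We chose a sample size of 80 patients based on estimates of patient need for access to T cell depleted grafts over 3-5 years".

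Section VII.3 sets out the TRM rule. The first look is at 10 patients, and then: "Otherwise the trial will continue according to the stopping rules plan (Appendix 2) up to a maximum of 73 patients". It gives a type I error of 0.05 and power above 80% at a true TRM of 15%, against an unacceptable rate of 30%. It adds: "Note the stopping rule must be made based on the chronological order of the patients enrolled". Appendix 2 lists one limit per row from 10 to 73 under the column heading "Patients Enrolled", and has no rows for 74 to 80.

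**The concern.** Two sections allow an 80th patient, while the stopping rule and its table end at the 73rd. All four places are current text, and none of these figures is redacted.

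After patient 73, the IRB and the medical monitor cannot tell from the document whether enrolling patient 74 complies with it. If 73 is the cap, VII.1 promises a sample that the rule does not permit. If 80 is the cap, the protocol's only numerical mortality stopping rule is silent for the last 7 patients.

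**Working it through.** **Inputs.** Enrolment ceiling 80 (IV.1a); sample size 80 (VII.1); maximum 73 (VII.3); 64 limits for rows 10 to 73, stopping when the count is at or above the limit (Appendix 2); unacceptable TRM 30%, favourable TRM 15%, type I error 0.05, power above 80% (VII.3).

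**The plan's own figures.** The null is TRM of 30% or more, so type I error is the probability of never stopping at 30%, and power is the probability of never stopping at 15%. An exact binomial recursion over the printed limits, with independent patients and a look after each patient from 10 to 73, gives 0.012 and 0.623. The stated 0.05 and above 80% are therefore not reproduced. That is a separate issue. It matters here only because the size of the gap depends on which probabilities are used.

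**Size of the gap.** 80 − 73 = 7 patients; 7/80 = 8.75% and 7/73 = 9.6%.

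**Is 80 simply 73 inflated for losses?** 73/(1 − d) = 80 requires d = 1 − 73/80 = 8.75%. A 5% loss gives 73/0.95 = 76.8, so 77. A 10% loss gives 73/0.90 = 81.1, so 82. No visible text states a dropout or non-evaluable rate.

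**Patients beyond the last row on the 80-patient reading.** If TRM were known at once, the expected number is 7 × P(pass row 73).

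| True TRM | P(pass row 73), printed table | Expected beyond row 73 | Using the figures stated in VII.3 |
|---|---|---|---|
| 15% | 0.623 | 7 × 0.623 = 4.4 | more than 7 × 0.80 = 5.6 |
| 20% | 0.295 | 7 × 0.295 = 2.1 | not stated |
| 25% | 0.080 | 7 × 0.080 = 0.6 | not stated |
| 30% | 0.012 | 7 × 0.012 = 0.1 | 7 × 0.05 = 0.35 |

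The gap is thus most likely to be reached when TRM is near the favourable rate, and least likely when TRM is unacceptable.

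**Can rows simply be added?** The prior and probability cut-offs are not given, so rows 74 to 80 cannot be rebuilt from the document. As an illustration only, assuming one constant limit over those rows, type I error and power would be 0.005 and 0.583 (limit 15), 0.008 and 0.610 (limit 16), or 0.010 and 0.620 (limit 17), against 0.012 and 0.623 as printed. The error rates therefore depend on the added limits and would need restating.

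**The case against.** The strongest reply is that the two numbers count different things: 80 enrolled, 73 counted for TRM. This is conceivable, because enrolment comes before conditioning ("Patients enrolled on this protocol will undergo evaluation for disease status and organ function per institutional HSCT guidelines prior to starting conditioning regimen") while TRM is counted after transplant, so some enrolled patients might never be transplanted. But the plan does not say this. The table heading and the ordering instruction in VII.3 both count patients enrolled, and no visible text defines an evaluable set, a replacement rule or a loss allowance. Some clinical sections are redacted, so this can be said only of visible text; the statistical section is not redacted. If this was the intent, it still has to be written down.

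A second reply is that a ceiling of 80 is respected by enrolling 73. That stands for IV.1a. It does not stand for VII.1, which calls 80 the chosen sample size.

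A third reply is that little is lost, and much of this stands. A reader might infer that patients 74 to 80 would have no mortality oversight. The documents do not support that. The medical monitor still meets the principal investigator about every 3 months and reviews subject deaths associated with the protocol, and on TRM "he/she will have the final authority regarding continuation of the study in the event of excessive TRM". Section VIII.1 also keeps an accrual hold: "If there are any attributable Serious Adverse Events, the study will stop accrual". Only the numerical trigger would be missing.

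**Conclusion.** The contradiction is real: the plan states a sample size that its own stopping rule does not permit, and no visible text reconciles the two. The consequence is modest. It concerns 7 patients, 8.75% of 80. On the 80-patient reading, the expected number enrolled past the last row is about 4.4 at 15% TRM and 0.1 at 30% from the printed table, or more than 5.6 and about 0.35 from the stated power and type I error.

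These numbers assume independent patients and TRM known at once. In fact TRM takes 100 days from transplant to establish, and enrolment comes earlier still, so they are approximate.

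A reader might also infer that the mismatch invalidates the error rates in VII.3, or explains why the printed table does not reproduce them. Neither follows. Seven further patients without looks leave the 73-patient test unchanged, and the failure to reproduce arises within rows 10 to 73.

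**What to change.** Reconcile IV.1a, VII.1, VII.3 and Appendix 2 by one of three routes, according to what was intended.

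- **(a) 73 is the cap.** State 73 in IV.1a and VII.1, and adjust the demand-based rationale in VII.1. Cost: two edited sentences.
- **(b) 80 is the cap.** Have the trial statistician regenerate Appendix 2 through row 80 from the original design parameters, and restate type I error and power for that table in VII.3. Cost: a rerun of the design, a new appendix and an edited VII.3.
- **(c) 80 are enrolled and 73 counted for TRM.** Say so, define which patients count, correct the enrolled wording in VII.3 and Appendix 2, and state how TRM is monitored in the others. Cost: a few sentences and a new column heading.

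Any route is a protocol change needing IRB approval under Section VIII. None needs more than the 80 patients already stated.

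### The Appendix 2 stopping table, applied as worded, has about 62% power at a 15% TRM rate, not the stated figure above 80%

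*Combined protocol and SAP*

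**What the plan says.** Section VII.3 (Stopping Rules) describes a predictive probability design for TRM. A rate of 30% or more is unacceptable and is tested one-sided. The stated properties are: "This design yields a type I error rate 0.05 and power greater than 80% when the true rate of TRM is 15"%.

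The boundary is worded in three places, each time so that reaching the listed number is enough to stop:

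- Section VII.3, first look: "If 3 or more out of 10 have a TRM the trial will stop".
- Section VII.3, later looks up to 73 patients: the trial stops if the count of TRM within 100 days is "ever greater than or equal to the number listed in the corresponding patients enrolled row the trial will stop".
- Appendix 2, column heading: "Stop if # with TRM within 100 days following HCT is greater than or equal to".

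Section VII.3 fixes the order of counting: "Note the stopping rule must be made based on the chronological order of the patients enrolled". On timing of review it says: "We plan to meet with medical monitor approximately every quarter to review these safety data and stopping rules". Crossing means that the trial stops and the treatment is declared not safe, although the medical monitor has the final say on continuation (VII.3 and VIII.1).

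**The concern.** Appendix 2 has 64 rows, one for each patient from the 10th to the 73rd, and the boundary is low at the start: 3 events stop the trial anywhere from 10 to 12 patients. With a true TRM of 15%, the expected count in the first 10 patients is 1.5, so 3 is not a rare result. A rule tested at every row from there on uses up its tolerance for false alarms early. It looked unlikely that more than 80% of trials with 15% TRM would pass all 64 checks.

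This is the plan's only numerical TRM boundary. The quoted power tells the IRB and the medical monitor how often the rule would condemn a treatment whose TRM is at the design's own favourable rate. A monitor deciding whether to override a crossing needs that rate to be right.

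**Working it through.** **Inputs**

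- Unacceptable rate 30%; favourable rate 15% (VII.3).
- Boundary c(n) from Appendix 2: 3 for n = 10–12; 4 for 13–15; 5 for 16–19; 6 for 20–23; 7 for 24–28; 8 for 29–32; 9 for 33–37; 10 for 38–41; 11 for 42–46; 12 for 47–52; 13 for 53–57; 14 for 58–64; 15 for 65–73.
- Stop if the count is at or above c(n) at any row, in enrolment order (VII.3 and Appendix 2).
- Assumed: patients are independent and every day-100 outcome is known.

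**Method**

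Let f(n, k) be the probability of k events among the first n patients with no crossing so far. Then

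f(n, k) = (1 − p) · f(n−1, k) + p · f(n−1, k−1),

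and from n = 10 any path with k ≥ c(n) is removed. Power is the sum of f(73, k) at p = 0.15. Type I error is the same sum at p = 0.30.

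**First rows by hand, p = 0.15**

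- n = 10: P(X ≥ 3) = 0.1798. The surviving paths include P(X = 2) = 0.2759 and P(X = 1) = 0.3474.
- n = 11: a third event adds 0.2759 × 0.15 = 0.0414; cumulative 0.2212.
- n = 12: the probability of standing at 2 after 11 patients is 0.2759 × 0.85 + 0.3474 × 0.15 = 0.2866. A third event adds 0.2866 × 0.15 = 0.0430; cumulative 0.2642.

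The n = 10 look alone is within a 20% allowance. By n = 11 the allowance is exceeded. The recursion then gives a cumulative crossing probability of 0.2989 by n = 20 and 0.3770 by n = 73.

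**Attempt to reproduce the stated figures**

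| Reading of the rule | Power at 15% TRM | Type I error at 30% TRM |
|---|---|---|
| Stated in VII.3 | above 80% | 5% |
| As worded: at or above c(n), every row 10–73 | 62.3% | 1.2% |
| Looks at n = 10 and n = 73 only | 74.4% | 1.9% |
| Stop only above c(n), every row | 81.6% | 3.2% |
| One look, at n = 73 | 87.6% | 2.6% |

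A simulation of 400,000 trials per rate in enrolment order agrees with the second row (62.3% and 1.2%). Under the worded rule, power reaches 80% only if the true TRM is about 11.7% or lower.

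**Quarterly review**

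If each meeting checks every row passed since the last one, nothing changes. If a meeting checks only the row it has reached, the number of looks depends on accrual. The sample size of 80 rests on "estimates of patient need for access to T cell depleted grafts over 3-5 years" (VII.1), so an assumed even accrual is 80/20 = 4.0 to 80/12 = 6.7 patients per quarter. Taking looks every 4 to 7 patients, a first look between n = 10 and n = 16, and a last look at n = 73:

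- power is 64.1% to 77.1% over all these schedules;
- power is 64.1% to 70.5% if the n = 10 look is kept, as VII.3 requires.

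Extra looks can only lower power, so 74.4% is the most that any schedule containing both n = 10 and n = 73 can reach.

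**The case against.** The strongest objection concerns how the table is used in practice. Its first column counts patients enrolled, not patients with a completed day 100. A monitor might therefore compare the deaths known on a given date with everyone enrolled by then. Because recent patients have had less time at risk, crossings become rarer. Simulation with even accrual of 16 to 27 patients a year, quarterly checks and a complete final check gives power of about 71% to 83% if deaths are spread evenly over the 100 days, and 78% to 86% if every death falls on day 100. This range straddles 80%. It depends on death-timing patterns that the documents do not give, and it sits badly with the instruction to apply the rule in order of enrolment. That instruction is best read as counting each outcome in the patient's own row, whenever it becomes known; the plan does follow everyone long enough for this: "All patients will be followed for primary and secondary endpoints for at least 100 Days following allogeneic HSCT" (VII.1). The objection shows that 62.3% is not the only figure one could compute. It does not make the stated power true of the rule as written.

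Three further points stand in the plan's favour.

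- The stated 0.05 can be read as a limit, and 1.2% respects it. Only the power claim fails outright.
- The discrepancy is protective: a 30% TRM rate would pass less often than stated.
- TRM is not the primary endpoint, the sample size does not rest on this power, and the monitor can let the trial continue after a crossing.

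Finally, the intended design may be sound. If the intended rule was to stop only above the listed numbers, both stated limits would be met. What is shown is a mismatch between the sentence and the worded boundary, not a design known to be underpowered.

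**Conclusion.** The concern holds. For the boundary as worded, power at 15% TRM falls about 18 points short of the stated minimum. The chance of a false alarm is nearly twice the most that the stated power allows (37.7% against 20%). The result is exact, given independent patients, complete day-100 outcomes and counting in enrolment order at every row. Checking only the current row at quarterly meetings does not bring it to 80% on any schedule examined. The readings that do exceed 80% each set aside part of VII.3. The documents do not show whether the power sentence or the boundary wording is the mistake. Because this is a stated property of the plan's only numerical TRM rule, it should be corrected despite the protective direction and the monitor's discretion.

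**What to change.** The sponsor's statistician should retrieve the original design output, recompute the exact operating characteristics, and reconcile the power sentence and first-look sentence in VII.3 with the heading of Appendix 2.

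- If the table as worded is confirmed, restate power as about 62% at 15% TRM and type I error as about 0.012.
- If a different boundary was intended, make the text and table match it and quote its computed values.

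Either way, state the look schedule and follow-up assumption behind the figures: whether every row is checked at each meeting, and whether a late outcome counts in the patient's own row. This review does not say which boundary is right.

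The cost is a protocol wording change and a short exact calculation, with no added patients or data. If the table is kept, the plan must quote a less favourable power.
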